#### 3.3 Test design

The current clinical investigation will use the algorithm developed in the DK007-ME investigation. It will be conducted as a double-blinded clinical investigation assessing the sensitivity and specificity of EDDI, an epilepsy alarm, for detection of GTC seizures in patients with epilepsy. The double-blinded part will be between the physicians annotating when GTC seizures exists based on EEG and video, the gold standard, and the epilepsy alarm, which annotates when GTC seizures exist based on the EMG signal.

Patients will be hospitalized at a specialized epilepsy center either to investigate suspected epilepsy or to improve their epilepsy diagnosis and treatment. During their hospitalization patients will at least be monitored by the gold standard: video monitoring and EEG.

In this investigation, approximately 20 patients with GTC seizures will be needed, along with approximately 10 patients with PNES. This means that probably 70-80 patients in total will be included and equipped with an EDDI, after providing their informed consent. The Epilepsy Alarm should be placed on one of the upper arms (the outer side of biceps) as shown in the IFU for the device. It will need to be replaced with a new electrode every 24 hours. After a maximum of 4 days, the patient will be discharged from the hospital, thus the investigation is finalized. During the investigation sEMG signals will be recorded through the EDDI, the seizure detections by the algorithm will be electronically annotated to compare against the times annotated by the staff based alone on the gold standard. The detections of the EDDI will be hidden for the clinical personnel until the end of the admission of the patient. When the admission of the patient has ended, the clinical personnel will remove an SD-card from the A-Unit, and ship it off to the device manufacturer, who will extract the seizure times, and sent them to the principal investigator.

The investigation will be conducted in accordance with the ethical principles that have their origin in the Declaration of Helsinki, ISO 14155 (2011) and the requirements of the local competent authorities.

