## 3.5.2 Secondary endpoints

- The specificity is calculated and evaluated indirectly as the false detection rate (the number of false detections per hour). A detection is categorized as a false detection, if it falls outside a seizure period (between start and end of a seizure, defined by the gold standard). Possible alarms during placement or removal of the device are discarded (this will only happen if the device is used wrong). All data (incl. video and EEG) are saved for each patient, which makes it possible to find the reasons for possible false alarms.
- Effect of the GTC seizure alarm in a nocturnal situation (23:00 07:00). The sensitivity will be calculated based on the data within this period of time (23:000 07:00) for each day.
- The nocturnal specificity will be calculated as the amount of false positives within the nocturnal period (23:00 07:00) for all days, with respect to the amount of hours.
- For each possible false alarm, the reason for it is checked to see if there is a reasonable explanation.
- The measure for whether the EDDI captures the PNES is calculated as the total number of PNES minus the number of captured PNES and divided by the total number of PNES. This means that a measure close to 100% ensures that the device will not alarm on PNES, and the closer the measure is to 0%, the more false alarms may come from PNES.

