## 9. Statistical considerations

#### 9.1 General considerations

A one group design is chosen due to the objective of estimation of sensitivity. No hypotheses are tested, but 95% two sided confidence intervals are constructed for the measure of sensitivity and specificity.

All patients enrolled who has been wearing the device, will be included in the Full Analysis Set (FAS) which forms the basis dataset for all analyses. No subgroup analyses are planned in advance. However if the final data end up showing equally distributed amounts of seizures from both kids and adults, we may study the result in the two subgroups.

The primary endpoint, the sensitivity, will be calculated as described in section 3.5.1 along with a 95% confidence interval (CI). The expectations for sensitivity (true positive assessments) are a lower limit of the two-sided 95% CI of more than  $95\% \pm 5\%$ .

The specificity is calculated and evaluate indirectly as the false detection rate (the number of false detections per hour). This parameter will be estimated along with 95% CI.

The effect of the GTC seizure alarm in a nocturnal situation (23:00 - 07:00) is found. Both the sensitivity and specificity will be calculated based on the data within this period of time (23:00 - 07:00) for each day and analyzed similarly to the analysis of the 24h periods.

Each false alarm is evaluated based on the video data to figure out, what may have caused it.

Adverse events (AEs) are summarized descriptively by type. Please refer to section 16 for details on AE collection types.

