#### 9.2 Sample size consideration for alarm correctness

With an expected sensitivity of 95%, a sample size of at least 19 patients with epileptic GTC seizures is needed. Based on this it has been chosen to include 20 patients with epileptic GTC seizures and furthermore 10 patients with PNES. To succeed in this inclusion, it is expected that about 80 patients will be included in total.

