#### 10.1 Data analysis

The data analysis will be performed by the principal investigator. The sensitivity and specificity of the device will be calculated. Furthermore the specificity will be calculated explicitly during night time.

For each false positive the EEG and video should be checked to see if there is an explanation for the false alarming.

Also for each GTC seizure that is registered by the alarm the latency should be calculated from the onset of the tonic phase of the GTC seizure.

For the patients with PNES it should be calculated how many of the seizures are registered by the alarm. The number is expected to be 0.

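### Section 3.5.2 says that a PNES measure near 100% ensures no alarms on PNES, which is more than about 10 PNES patients can show

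*Protocol*

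**What the plan says.** Protocol section 3.5.2 (Secondary endpoints) gives the PNES measure as a proportion of seizures, "calculated as the total number of PNES minus the number of captured PNES and divided by the total number of PNES". The next sentence interprets the two ends of the scale. At the favourable end, "a measure close to 100% ensures that the device will not alarm on PNES". At the other end, values nearer 0% mean that more false alarms may come from PNES.

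The number of PNES patients is given twice without a derivation or a precision target: "along with approximately 10 patients with PNES" in section 3.3, and "furthermore 10 patients with PNES" in section 9.2. Section 10.1 asks for the number of PNES registered by the alarm and adds: "The number is expected to be 0".

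Section 9.1 describes an estimation study ("No hypotheses are tested") in which "95% two sided confidence intervals are constructed for the measure of sensitivity and specificity". Specificity there means false detections per hour, which is a different quantity from the PNES measure. Nothing elsewhere in the protocol qualifies the word *ensures*.

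**The concern.** The sentence moves from a point estimate in a small sample to an assurance about how the device behaves. It fails in two ways. By the formula itself, any value below 100% records an alarm on at least one PNES, so a value merely close to 100% cannot assure that there are none. Statistically, even a value of exactly 100% from about 10 patients leaves a sizeable alarm rate possible.

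The point matters because telling GTC seizures from non-epileptic convulsive seizures is part of the stated purpose (section 3.2), a secondary objective (sections 3.4.2 and 7.1.2) and a named secondary outcome (section 8.1). Section 2.1 presents the study as confirmatory of the product's reliability. If the expected zero alarms are seen, a report that repeats the protocol's wording would claim more than the data can carry.

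**Working it through.** **Inputs from the protocol.** About 10 PNES patients (sections 3.3 and 9.2); 0 captured PNES expected (section 10.1); two-sided 95% as the confidence level used elsewhere (section 9.1).

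**The plan's own figure.** The 10 PNES patients come with no inputs, so there is nothing to reproduce. The only derived number is for the other group: "With an expected sensitivity of 95%, a sample size of at least 19 patients with epileptic GTC seizures is needed". It can be recovered as 1.96² × 0.95 × 0.05 / 0.10² = 18.2, rounded up to 19, but only by assuming a half-width of 10 percentage points. A half-width of 5 points would give 73. Neither calculation says anything about the PNES group.

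**Patient level, zero alarms.** The exact (Clopper-Pearson) two-sided 95% upper limit for 0 of n is 1 − 0.025^(1/n). With n = 10 this is 1 − 0.025^(0.1) = 0.308, or 30.8%. The lower limit for the share of patients without an alarm is therefore 69.2%. Other methods give similar values: Wilson 27.8%, rule of three 3/10 = 30%, one-sided exact 1 − 0.05^(0.1) = 25.9%.

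**How easily zero alarms can arise.** If 10% of PNES patients would truly have an alarm, the chance of none in 10 is 0.9^10 = 34.9%. If 20% would, it is 0.8^10 = 10.7%.

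**A value close to 100%.** With one PNES per patient and 1 alarm in 10, the measure is 90%. The exact 95% interval for the alarm share is then 0.3% to 44.5%.

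**Seizure level, the unit of the planned measure.** Write m for PNES per patient and ICC for the within-patient correlation. Both are assumptions, because the protocol gives neither. As an approximation, the effective number of events is 10m / (1 + (m − 1) × ICC), which replaces n in the formula above. With zero alarms:

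| m | events | upper limit, ICC 0 | ICC 0.5 | ICC 1 |
|---|---|---|---|---|
| 2 | 20 | 16.8% | 24.2% | 30.8% |
| 3 | 30 | 11.6% | 21.8% | 30.8% |
| 5 | 50 | 7.1% | 19.9% | 30.8% |

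The range is about 7% to 31%.

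**Scale of the gap.** An upper limit of 10% or less after zero alarms needs 36 independent events (ln 0.025 / ln 0.90 = 35.01, rounded up). A limit of 5% or less needs 72 (ln 0.025 / ln 0.95 = 71.9, rounded up).

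**The case against.** The strongest reply is that the sentence only explains the scale. It follows the formula, covers both ends, and attaches no threshold, success criterion or conclusion. Section 9.1 rules out hypothesis tests, and the objectives speak only of investigating. This largely stands. A reader might infer that the plan contains a decision rule under which the trial must declare that the device does not alarm on PNES. The protocol has no such rule. What remains is a literal assurance that nothing else in the text tempers.

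A second reply concerns the interval. A reader might infer from section 9.1 that the PNES measure will be reported without one. The section does not name an interval for it, but does not exclude one either, and a confidence interval for a secondary proportion can be left to the SAP. That silence is not counted as a defect here. An interval added in the SAP would, however, sit beside a protocol sentence that contradicts it.

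A third reply is about units. The 30.8% is the share of patients with an alarm, whereas the endpoint counts seizures. This is correct. A reader who took 31% as the limit for the planned measure would be taking the least favourable end of a range that rests on assumed inputs. The lower end, 7.1%, requires five PNES per patient that behave as independent events. The limit is above zero throughout the range, so the objection changes the size of the uncertainty and not the conclusion about the wording.

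**Conclusion.** The point holds as an overstated interpretation of a secondary endpoint. The formula and the planned number of patients are not in error. With 10 PNES patients and no alarms, the data would still be compatible with alarms in up to 30.8% of such patients (exact, two-sided 95%). For the per-seizure measure the limit is about 7% to 31%, given 2 to 5 PNES per patient and a correlation of 0 to 1, all assumed. Any value below 100% contradicts the assurance outright. The primary endpoint is unaffected, and so are the point estimate and the count of captured PNES. The correction is minor.

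**What to change.** In section 3.5.2, replace the clause "a measure close to 100% ensures that the device will not alarm on PNES" with wording such as:

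> A measure close to 100% indicates that few of the observed PNES triggered an alarm. It is reported as an estimate with a two-sided 95% CI that allows for several PNES per patient, together with the number of PNES patients with at least one alarm and its exact 95% CI, and not as proof that no PNES will trigger an alarm.

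The patient-level count is useful because, if no alarm occurs, the within-patient correlation cannot be estimated from the data. The exact interval by patient needs no assumption about it.

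Do not write a fixed 31% into the protocol: section 3.3 makes the number of PNES patients only approximate, and the limit moves with it. Keep the formula and the 10 patients.

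The cost is one sentence of protocol text, one extra interval and a less favourable conclusion. No further patients or data are needed.

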## 3.5.3 Investigation population

#### **3.5.3.1 Inclusion criteria:**

- 1) Patients referred to video-EEG monitoring (for more than 24 hours).
- 2) Data in patient history suggesting a convulsive epileptic or non-epileptic (PNES) event.
- 3) Males and females aged 3-80 years.
- 4) Patients who can linguistically and mentally participate in the opinion of the investigation.
- Following receipt of verbal and written information about the investigation, the patient must provide signed informed consent before any investigation related activity is carried out. Considerations regarding patients who are mentally retarded are described in section 17.

#### **3.5.3.2 Exclusion criteria:**

- 1) Suspicion that a patient does not have convulsive epileptic or non-epileptic (PNES) events
- 2) Pregnancy
- 3) Patients known or suspected of not being able to comply with a study protocol (e.g. due to alcoholism, drug dependency or psychological disorder)
- 4) Patients with allergy to the adhesive plaster used to fix the device to the body
- 5) Patients that are involved in other studies.

## 3.5.4 Investigation design

First Patient planned to be included: 1st of February 2014

Last Patient planned to complete investigation: 31st of October 2014.

#### **3.5.5 Investigational device**

The investigational device is a wireless device (EDDI) that is placed on the upper arm, and measures sEMG. IctalCare have designed an algorithm, which is part of the EDDI. This algorithm will detect GTC epileptic seizures. For more information see section 4. The device is CE marked for detecting GTC epileptic seizures on patients aged 3-80.

#### 3.5.6 Flow chart

Table 1 Flow chart

Assessment	Screening	Inclusion	Data collection	End of investigation
Day	<21 days prior to inclusion	1	1-5	1-5
Information to patients and caretakers	Х			
Informed consent	Х	Х		
Eligibility criteria		Х		
Demographics		Х		
Type and frequency of seizures		Х		
AEs (each day)			Х	Х
Gold standard monitoring (video + EEG)			Х	Х
EDDI (every 24 hours, changed at the same			Х	Х
time each day)				
Details on convulsive seizures (time – abnormalities?)			Х	Х

Figure 1 Schematic diagram of investigation

## 4. Identification and description of the investigational device

## 4.1 Summary description of the investigational device

The wireless medical device class I holds a CE mark. It is named EDDI (Epileptic seizure Detector Designed by IctalCare) and is designed to alarm of GTC epileptic seizures. IctalCare has designed an algorithm, which is implemented in EDDI. This algorithm will make it possible to detect the GTC epileptic seizures.

w

4.2	Details	on EDDI	
-----	---------	---------	--

sEMG Patient Unit (2 pieces)

The active part, which is placed on the patient
during the clinical investigation, is called a
patient unit. It consists of two units: an electrode
(the plaster) and Senses (the case with the
electronics). During the clinical investigations
each patient will be wearing one patient unit
placed on one of the upper arms. Every 24 hours
the electrode and the battery in Senses must be
exchanged with new ones.
The electronic consists of columb three concerns

The electrode consists of gel with three sensors for measurements of bio-signals. It may be used up to 24, and be relocated three times within the 24 hours. (Single patient use only). Afterwards it is disposable.

Senses contains electronics for measuring and processing the sEMG signal. The Senses device includes a microprocessor, a frontend, and memory and data storage capability. Furthermore it includes an 868MHz radio, to communicate with the A-Unit. The Senses includes software (SW) that calculates on all the sEMG data, using the seizure algorithm. All seizure events are stored locally and sent via radio to the A-Unit.

A-Unit

Senses

The A-Unit contains a 868MHz radio and communicates with the Senses. All information on the seizure events is stored in the A-Unit. The A-Unit contains software which makes sure that the seizure events are time stamped.

#### Battery

Batteries: The Senses needs one CR2450 type battery. The battery will be exchanged every day.

#### **4.2.1 Design properties**

EDDI consists of a soft and flexible plaster, electrode, and an active device, Senses. The electrode is designed, to be easily placed on the patient's upper arm, and so that the patient notices the device as little as possible, while it is mounted on the arm. Senses is connected to the electrode with three buttons in a way, which aims at making it unnoticeable to the patient. All material used in the electrode are known to be biocompatible. The high tack multi-purpose hydrogel makes the electrode easy to remove without discomfort for the patient.

The casing of Senses is designed to fit to the new electrode. The Senses contains no SD-card, the data is time stamped and transferred wirelessly via a radio link to the A-Unit, where it is stored on an SD-card.

#### 4.2.2 Materials

Only the electrode is in direct contact with the skin of the patient. This electrode has been tested and validated by the manufacturer, and holds a CE mark.

#### 4.2.3 Biological components or biologic active materials

No biologic materials are used.

#### 4.2.4 Installation, use, control and removal

The EDDI is delivered in a box. The use of the system is described in the "Instruction For Use". The Senses is placed on the patient as described in the IFU, and the two devices are turned on to start the surveillance of the patient. The mounting of the Senses is done by the investigator or a study nurse after instructions by the investigator.

At the end of a trial the Senses is removed from the patient, the electrode is trashed, and the EDDI system is packed away in the allocated box, when the SD-card has been removed from the A-Unit and sent to IctalCare, and a new SD-card has been placed in the A-Unit.

#### 4.2.5 Training and experience

Before the investigation is initiated the staff members in the EMU are instructed by personnel from IctalCare in the preparation, use, control and removal of the system. Furthermore they are shown how to remove the SD-card and replace it by a new one.

#### 4.2.6 Medical procedure

In the investigation all surveillance monitoring of the patients in the EMU is performed as usual, when a patient is admitted for 24 hours surveillance or more in relation to a diagnosis or improvement of the treatment.

#### 4.2.7 Known and potential risks

As the patients are under surveillance according to the normal clinical setting, the only risks are the ones related to the use of EDDI, which are addressed in section 4.2.8.

#### 4.2.8 Results of the risk analysis

A risk management analysis was conducted as part of the design and development process with respect to the guidelines in *ISO14971*: "A risk management plan was included as part of the design and development plan. Product characterization and hazard analysis were performed. Two separate risk analyses were performed for use, and design and manufacturing risks. Finally a risk management report was concluded".

## 5. Justification for the design of the clinical investigation

Epilepsy is a common serious neurological condition with a prevalence of 0.8-1.0%. People with epilepsy find it helpful to consider safety aids or equipment that might help them with day-to-day life. For example, an alarm that can alert family or friends when someone has a seizure, or a safety pillow if they have seizures while asleep. IctalCare developed EDDI, a wireless alarm (in the form of a plaster) that is able to detect GTC seizures in epileptic patients.

In a clinical investigation (DK007-ME) an algorithm, which made it possible to detect GTC seizures, was developed. It was first tested in IRIS, a predecessor for EDDI, in a second clinical investigation (DK006-ME). IRIS was used on 13 patients with epilepsy to measure sEMG. GTC seizures were confirmed by the gold-standard (video monitoring and EEG recordings) for four patients, and the algorithm proved efficient. No SADE, nor SAEs, nor device deficiencies that might have led to a SAE were reported.

# 6. Risks and benefits of the investigational device and clinical investigation

Based on the risk management analysis (see section 4.2.8), no known risks are expected during the trial. Only exception: as some patients are allergic to standard plasters, some patients may as well be allergic to the gel used on the electrodes.

There are no known benefits.

## 7. Objectives and hypotheses of the clinical investigation

#### 7.1.1 Primary objective

• To investigate the sensitivity of EDDI's ability to detect GTC seizures.

#### 7.1.2 Secondary objectives

- To investigate the specificity of EDDI's ability to avoid false alarms.
- To investigate reasons for possible registered false alarms.
- To investigate the latency of the seizure detection by the EDDI compared to the actual start of the GTC seizure.
- To investigate the EDDI's ability NOT to detect PNES which visually look like GTC seizures.

#### 7.1.3 Hypothesis

From previous results on the same type of data (sEMG) it is expected that the sensitivity and FDR of this study will be comparable those previous ones. The differences lie within the newer version of the device (EDDI) measuring the sEMG signal. The software is the same as used in IRIS, and most of the hardware as well. The electrode is different, but clinical tests have shown that the newer electrode provides a signal-to-noise ratio (SNR) which is equally good or better compared to the older version of the electrode (used with IRIS in DK006-ME).

## 8. Design of the clinical investigation

#### 8.1 General

The investigation is designed as an assessor controlled double-blinded clinical investigation assessing the sensitivity and specificity of EDDI, in detection of GTC seizures in epileptic patients. As a secondary outcome the study furthermore tests EDDI's ability NOT to alarm on PNES.

The assessor is a physician at the site(s) and will provide details on seizure type and time, based upon the gold standard: video monitoring and EEG. The EDDI will not provide a visual or audible indication whether an alarm has occurred. In this way, the assessor will remain blinded to the alarms set by EDDI. The EDDI works in real time and will thereby be blinded from the annotations by the clinical personnel.

The seizure times obtained by the EDDI will be transferred to a computer. This data has an audit trail and cannot be changed.

